7.1.2.6 SARS-CoV-2 PCR

The CDC Influenza SARS-CoV-2 (Flu SC2) Multiplex Assay will be used to measure active COVID-19. During the test, the subject is asked to tilt the head back 70 degrees. While gently rotating the swab, a 6-inch swab is inserted less than one inch into nostril (until resistance is met at turbinates).

7.1.2.7 The Fatigue severity scale

The fatigue severity scale³³ is a measure of fatigue that contains 10 items. The subjects will be instructed to respond to each statement using a scale of 1 to 7, with 1 indicating "Strongly Disagree" and 7 indicating "Strongly Agree."

7.1.3 Daily Outcomes

7.1.3.1 Daily activity and sleep tracking

Randomized, Placebo-Controlled Parallel Group Clinical Trial of Nicotinamide Riboside to evaluate NAD+ Levels in Individuals with Persistent Cognitive and Physical Symptoms After COVID19 Illness ("Long-COVID")

Version 1.1

Each subject will be provided with a Fitbit Charge 4 that they will wear throughout the study. The device will track the participant's heart rate, activity, and sleep. The subject will be instructed to wear their device at all times, except for when it is being charged and when they are bathing. HC and long-COVID participants will not be given a FitBit.

7.1.3.1.1 Charging and syncing procedures

Subjects will be instructed to ensure that the device is charged at all times. The subject will be instructed to charge their device when their battery is low (roughly once every 4 days) during a period of inactivity, such as when watching TV. The subject will be explicitly instructed not to charge their device during times of sleep. The subject will be instructed to sync their device at least 3 times per week. Charging and syncing compliance will be routinely monitored by a study coordinator. The coordinator will conduct periodic reviews of the subject's charging and syncing compliance by logging onto the subject's Fitbit dashboard. If the device has not been appropriately charged or synced, the study coordinator will contact the subject to remind them to sync or charge their device as needed. If a subject requires more than three such reminders, they will be considered non-compliant, and the PI will determine if the subject should continue in the study or if their study participation should be discontinued.

7.2 Training and Validation

All evaluators must be certified by the study PI to perform cognitive and psychiatric outcome assessments. It is strongly preferred that a single evaluator performs all measures with a given instrument throughout the study, if possible.

8. INTERVENTIONS ADMINISTERED

8.1 INTERVENTION

8.1.1 Study Product Description

Niagen® is a commercially available form of nicotinamide riboside (NR) manufactured by ChromaDex, Inc. Niagen® is generally recognized as safe (FDA GRAS Notice No. 635) for use in a variety of media, including vitamin waters, protein shakes, and powdered beverages. Niagen® has five issued process and use patents in the United States and several others internationally.

Chemical Structure of nicotinamide riboside:

8.1.2 Drug and Placebo

Chromadex Inc. will provide 250 mg capsules. Identical appearing capsules with only filler will be prepared as placebo.

Randomized, Placebo-Controlled Parallel Group Clinical Trial of Nicotinamide Riboside to evaluate NAD+ Levels in Individuals with Persistent Cognitive and Physical Symptoms After COVID19 Illness ("Long-COVID")

Version 1.1

8.1.3 Acquisition

When the study intervention shipment arrives at the site, the person accepting the shipment must perform an inventory and fill out a supplement receipt log. The contents of the shipment must be counted, verified, and inspected for damage. Any damaged shipments will be documented. The study supplement will be picked up from MGH Clinical Trials Pharmacy on the same day it will be dispensed. Detailed logs will be kept recording quantity of supplement dispensed and study staff in charge of supplement transport and dispensing.

8.2. Product Storage and Stability

Niagen NR is found to be stable under ambient conditions of 25 °C and 60% relative humidity for 11 months in a solid, powdered form.

8.3 Dosage, Preparation and Administration of Study Intervention

Niagen NR 1000 mg (four capsules) or PBO (four capsules) should be taken orally twice daily with food. The capsules should be swallowed whole.

8.4 Modification of Study Intervention for a Subject

Dosing may be suspended at any time by the PI or designated licensed clinician sub-investigator. This will be documented along with the reason(s) and dates of adjustment in the CRF for each subject requiring this manipulation. The PI or designated licensed clinician Sub-Investigator may suspend the dosage of study dietary supplement or discontinue the study supplement for AEs thought to be related to the study supplement or for other reasons during the trial (the reason and dates of suspension or dose suspension must be documented in CRF). If the AE is mild or moderate, the dosage may be re-started after the event improves. If the AE is serious or life threatening and deemed to be definitely related to the dietary supplement, the study dietary supplement will be discontinued immediately. Study subjects must remain off the study dietary supplement permanently. Subjects may not resume study dietary supplement. All AEs will be followed to resolution.

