11.4.1 Assessment of Adverse Events

At each visit (including telephone visits), the subject will be asked if they had any problems or symptoms since their last visit in order to determine the occurrence of adverse events. If the subject reports an adverse event, the Investigator will probe further to determine:

- Type of event
- Date of onset and resolution (duration)
- Severity (mild, moderate, severe)
- Seriousness (does the event meet the above definition for an SAE)
- Causality, relation to investigational protocol
- Outcome

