11.4.2 Relatedness of Adverse Event to Investigational Protocol

1. Not Related:	Concomitant illness, accident, or event with no reasonable association with protocol.			
2. Unlikely:	The reaction has little or no temporal sequence from administration of the investigation			
	protocol, and/or a more likely alternative etiology exists.			
3. Possibly Related:	The reaction follows a reasonably temporal sequence from administration of the investigational protocol and follows a known response pattern to the suspected investigational protocol; the reaction could have been produced by the investigational protocol or could have been produced by the subject's clinical state or by other modes of therapy administered to the subject.			

Randomized, Placebo-Controlled Parallel Group Clinical Trial of Nicotinamide Riboside to evaluate NAD+ Levels in Individuals with Persistent Cognitive and Physical Symptoms After COVID19 Illness ("Long-COVID")

Version 1.1

4. Probably Related:	The reaction follows a reasonably temporal sequence from administration of investigational protocol; is confirmed by discontinuation of the investigational protocol or by re-challenge; and cannot be reasonably explained by the known characteristics of the subject's clinical state.
5. Definitely Related:	The reaction follows a reasonable temporal sequence from administration of investigational protocol; that follows a known or expected response pattern to the investigational protocol; and that is confirmed by improvement on stopping of the investigational protocol, and reappearance of the reaction on repeated exposure.

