11.4.3 Recording of Adverse Events

All clinical adverse events are recorded in the Adverse Event (AE) Log in the subject's study binder. Study staff should fill out the AE Log and enter the AE information into the EDC system within 48 hours of learning of a new AE or receiving an update on an existing AE.

Entries on the AE Log (and into the EDC) will include the following: name and severity of the event, the date of onset, the date of resolution, relationship to investigational product, action taken, and primary outcome of event.

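### The compulsory permanent stop in Section 8.4 cannot be triggered by the first occurrence of a serious reaction, and its restart permission covers serious AEs of mild or moderate severity graded below Definitely Related

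*Combined protocol and SAP*

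**What the plan says.** Section 8.4 first gives the PI or a delegated clinician discretion to suspend or discontinue dosing. Two fixed rules follow.

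- Restart: "If the AE is mild or moderate, the dosage may be re-started after the event improves".
- Compulsory stop: "If the AE is serious or life threatening and deemed to be definitely related to the dietary supplement, the study dietary supplement will be discontinued". This takes effect at once, and the participant then stays off it permanently: "Subjects may not resume study dietary supplement".

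Section 11.4.2 grades relatedness in five categories. The upper three are:

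- Possibly Related (category 3): reasonable timing, and the reaction "follows a known response pattern to the suspected investigational protocol".
- Probably Related (category 4): reasonable timing, the reaction "is confirmed by discontinuation of the investigational protocol or by re-challenge", and the participant's clinical state does not reasonably explain it.
- Definitely Related (category 5): reasonable timing and a known or expected pattern, "that is confirmed by improvement on stopping of the investigational protocol, and reappearance of the reaction on repeated exposure".

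Section 11.4.1 records severity (three levels) and seriousness as separate items. Section 11.3.2 makes an AE serious if it needs hospital admission, whatever its severity.

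**The concern.** The rule is meant to act at once and to prevent re-exposure, yet its trigger is a grade that can be awarded only after a stop and a re-exposure. It is therefore unavailable at the point where it is most needed. The restart sentence is also written on a different axis (severity) from the stop sentence (seriousness), so the two do not divide events cleanly.

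What is at stake is participant safety and consistent handling. Two participants with the same first serious suspected reaction could be treated differently. One who was admitted to hospital with an event of moderate severity could be restarted within the wording of 8.4. A dependable fixed rule has value here because safety monitoring rests with the PI and co-investigators (Sections 11.2 and 11.3.1), and treatment codes are requested only after database lock (Section 9.1.3).

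**Working it through.** The plan states no figure on this point. The check substitutes the 11.4.2 definitions into the 8.4 rules.

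**Step 1. The trigger.** Compulsory stop = (serious or life threatening) AND (definitely related).

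**Step 2. Which related grades can be reached, and when.** Each entry assumes that the other elements of the grade are met.

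| Stage | Event with a known response pattern | Unexpected event, no known pattern |
|---|---|---|
| Onset, dosing not yet stopped | Possibly | none |
| Stopped and improved | Possibly, Probably | Probably |
| Reappeared on re-exposure | Possibly, Probably, Definitely | Probably |

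The second column matters because Possibly and Definitely both ask for a recognised pattern and Probably does not. Section 10.1.1 lists only five reported NR reactions: four labelled mild, plus increased bruising. A serious reaction may well match none of them. Read literally, it then has no related grade at onset.

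**Step 3. Apply both 8.4 rules.**

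- (a) First occurrence of a serious reaction, with no earlier stop and restart: the highest grade is Probably Related, so the compulsory stop is not triggered.
- (b) A reaction that improved off supplement and returned on restart: Definitely Related can be met and the stop is triggered, but only after re-exposure. This includes an earlier non-serious episode that returns as a serious one.
- (c) Serious, mild or moderate, and graded anywhere from Not Related to Probably Related (four of the five grades): the restart sentence applies and nothing in 8.4 bars it.
- (d) Serious, severe, and graded below Definitely Related: neither fixed rule covers it, so the PI decides.
- (e) Serious, mild or moderate, and Definitely Related: both sentences apply on their face, and the ban on resuming should prevail.

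**Step 4. Other routes to a stop.** Section 5.4 requires discontinuation if an AE makes continuing contrary to the participant's interest, or if an exclusion criterion is newly met. Clinical-trial exclusion 8 (a significant illness bearing on safety) and exclusion 11 (known hypersensitivity to NR) could apply, and the schedule in 6.1 reviews eligibility at each visit from Week 0 to Week 22. Sections 8.4, 8.4.1 and 11.3.1 allow a discretionary stop. Sections 11.3.2 and 11.5 add PI review and 24-hour SAE reporting, which are review and reporting duties rather than dosing rules.

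**The case against.** The strongest reply is that the protocol already stops such participants. This stands in part. A reader might infer that no compulsory stop exists at a first serious reaction, or that a participant must be re-exposed before being taken off. The documents support neither reading. Both bullets of 5.4 cited above are mandatory, the exclusion route needs no causality grade, and dosing can be suspended at any time. But that route catches only reactions that match a listed criterion, blinding limits what hypersensitivity can be known, and safety labs are scheduled only at screening. It does not make the trigger in 8.4 work.

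A second reply is that 8.4 does not cite 11.4.2, which grades relation to the investigational protocol rather than to the supplement. That is true, and a PI applying the everyday sense of the word could act at once. However, 8.4 uses the name of the scale's top category, no other definition is given, and Section 11.4.3 has the AE log record "relationship to investigational product, action taken, and primary outcome of event". Leaving two readings open is itself a cause of inconsistent handling.

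A third reply reads 8.4 as a ladder in which mild or moderate events sit below serious or life-threatening ones without overlap. That is a possible reading and would close the restart gap, but Sections 11.3.2 and 11.4.1 treat seriousness as separate from severity. It would not cure the trigger. Restart is also only permitted, never required.

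**Conclusion.** The point holds, within limits. Read with the only relatedness scale provided, the 8.4 stop and ban on resuming cannot be triggered by the first occurrence of a serious reaction that has had no earlier stop and restart. Serious AEs of mild or moderate severity graded below Definitely Related fall within the restart permission.

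Two broader statements would be wrong. A first serious episode can trigger the rule if an earlier episode resolved off supplement and returned on restart (case b). A serious AE of mild or moderate severity already graded Definitely Related is barred from restart (case e).

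The conclusion assumes that 8.4 uses the term as 11.4.2 defines it and that serious has its 11.3.2 meaning. The documents give no rate of serious related AEs, so no count of affected participants is possible. The other safeguards reduce the risk, but the rule is wrong as written and should be amended.

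**What to change.** Amend 8.4 in two places.

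1. Replace the definitely-related condition with *at least possibly related (11.4.2 categories 3 to 5)*, and add that an unexpected serious event is not exempt for lack of a known response pattern.
2. State that the restart sentence does not apply to a serious AE judged at least possibly related. Restart after a serious AE judged not related or unlikely related stays with the PI.

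Lowering the trigger only to Probably Related would restore the ban on resuming once the event improves off supplement. It would not give an immediate stop, because that grade itself needs discontinuation or re-challenge.

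**Cost.** This is a short amendment with no change to enrolment or analysis method. Judgement remains at the boundary between Unlikely and Possibly. A few participants may be stopped permanently for events the supplement did not cause, some of them on placebo. The visit schedule gives the likely placebo share of such stops. Weeks 2 to 22 are 20 weeks.

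- NR: 60 × 20 + 40 × 10 = 1,600 person-weeks.
- Placebo: 40 × 10 = 400 person-weeks.
- Placebo share after baseline: 400 / 2,000 = 20%.
- With the two-week lead-in for all 100 participants: (400 + 200) / 2,200 = 27%.

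If serious events not caused by the supplement arise, and are graded possibly related, at the same rate per week on placebo and NR, about 20% to 27% of such stops would fall on placebo. These shares ignore dropout. They describe the side effect of the fix, not the size of the defect.

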8.4.1 Dosage Discontinuation

Reasons for discontinuation of study dietary supplement may include an AE or PI recommendation, protocol deviation, loss-to-follow-up, patient request, or death. All serious adverse events (SAEs) that occur in a subject who has discontinued early must be recorded and reported within 24-hours of awareness. Study subjects who discontinue study dietary supplement prematurely (early discontinuation from study) and decide not to remain in the study will be encouraged to return for an Early Termination Visit.

8.5 Assessment of Subject Compliance

Subjects will be instructed to return empty and unused study dietary supplement containers at each clinic visit or the Early Discontinuation Visit. Research staff will review returned and unused study dietary supplement and log information into the reconciliation form to determine compliance. Non-compliance will be defined as taking less than 80% or more than 120% of study agent as determined by unused capsule counts. If a study subject is non-compliant with study dietary supplement, research staff should re-educate and train the subject in administration of study agent. If the subject's non-compliance persists, it will be left up to the PI to determine whether the subject should be discontinued from the study.

9. STATISTICAL ANALYSIS

Descriptive statistics will be used to characterize the cohort's demographic and clinical variables. We will conduct independent sample t-tests to examine between-group differences in demographic variables at baseline and analysis of variation (ANOVA) to test for between-group differences in treatment compliance for each study visit.

Randomized, Placebo-Controlled Parallel Group Clinical Trial of Nicotinamide Riboside to evaluate NAD+ Levels in Individuals with Persistent Cognitive and Physical Symptoms After COVID19 Illness ("Long-COVID")

Version 1.1

9.1 Primary analysis

For all outcomes, we will perform intention-to-treat (ITT) analysis and mixed-effects model repeated measures (MMRM). Group (NR-NR vs. PBO-NR sequence), time, and group by time interactions will be included in the MMRM as fixed effects. The study's outcomes will be the change score of ECog, RBANS, and TMT-B from baseline, and the change in NAD+ levels from baseline. We also will examine changes in the FSS, BAI, BDI, and PSQI scores. An unstructured covariance matrix will be used to account for the correlation of repeated measures within a participant. Age, sex, and education will be included in the models as covariates.

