3. SPECIFIC AIMS

3.1 Overall Study Design and Plan

The study uses a double-blinded, placebo lead-in, randomized, parallel group, PBO-controlled design. For this clinical trial, one-hundred individuals over 17 years of age meeting operationalized criteria for Long-COVID will be recruited. These 100 participants will undergo a placebo lead-in period of two weeks. Sixty participants will then be randomized to NR (TruNiagen®, Chromadex) 1000 mg twice daily for 22 weeks, and 40 will receive placebo for the next 10 weeks followed by NR for 10 weeks. Outcomes will consist of standardized cognitive, neuropsychiatric, physical, functional and biomarker assessments as well as daily sleep and activity monitoring with wearable actigraphy.

Randomized, Placebo-Controlled Parallel Group Clinical Trial of Nicotinamide Riboside to evaluate NAD+ Levels in Individuals with Persistent Cognitive and Physical Symptoms After COVID19 Illness ("Long-COVID")

Version 1.1

The study will also help better understand the nature of long-COVID by comparing this group with a healthy control group of individuals who were infected with COVID-19 but fully recovered. To better address this aim, we will also increase our sample size of individuals with long-COVID by testing individuals with long-COVID ages 18 and older who will only complete 1 visit. Comparing these groups will help establish differences in NAD+ levels at baseline associated with long-COVID, as well as help elucidate the cognitive profile, neuropsychiatric and physical functioning, and markers of glia and neural functioning in this population. Participants in these additional cohorts will only complete one visit and will not be administered NR or PBO.

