5.3 Randomization

Subjects in the clinical trial will be randomized into one of two groups (see Figure 4 below). Randomization will be done by MGH Clinical Trials Pharmacy.

Screening (Week 0)	Baseline (Week 2)	Visit 1 (Week 7)	Visit 2 (Week 12)	Visit 3 (Week 17)	Visit 4 (Week 22)	Follow-up (Week 24)
Placebo (Lead-in)	N = 60 NR N = 100	NR	NR	NR	NR	
Placebo (Lead-in)	N = 100 $N = 40$ Placebo	Placebo	NR	NR	NR	

Figure 4. Study Schema

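### The MMRM on change from baseline does not adjust for the baseline value of the outcome, which costs precision and leaves chance baseline imbalance in the estimate

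*Combined protocol and SAP*

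**What the plan says.** Section 9.1 (Primary analysis) takes as response the "change score of ECog, RBANS, and TMT-B from baseline, and the change in NAD+ levels from baseline", and applies the same approach to FSS, BAI, BDI and PSQI. On the model it says: "Group (NR-NR vs. PBO-NR sequence), time, and group by time interactions will be included in the MMRM as fixed effects". It adds: "Age, sex, and education will be included in the models as covariates". On the covariance it says: "An unstructured covariance matrix will be used to account for the correlation of repeated measures within a participant".

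No other section brings in the baseline value of the outcome. The only other covariate list, for the exploratory regressions in 9.1.2, has age, sex, education and time since acute infection. Section 9 plans baseline comparisons between the arms for demographic variables only. Section 3.1 sets the allocation: "Sixty participants will then be randomized to NR", while "40 will receive placebo for the next 10 weeks followed by NR for 10 weeks". On the method, section 5.3 says only that "Randomization will be done by MGH Clinical Trials Pharmacy", and it mentions no stratification.

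**The concern.** A change score subtracts the whole baseline value, so the slope on baseline is forced to 1. When baseline and follow-up correlate at less than 1, this over-corrects: participants with poor baselines tend to move back toward the mean whatever they receive. There are two consequences.

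- **Precision.** Baseline noise that a fitted slope would remove stays in the residual variance. That matters in a trial of 100 split 60:40.
- **Dependence on chance imbalance.** If one arm starts worse by chance, it will appear to improve more. No stratification is described that would limit this. If an imbalance in baseline ECog or RBANS appears after unblinding, adding baseline then would be a post hoc choice.

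The unstructured covariance does not help. The response is a change score, which is zero for everyone at baseline, so the baseline value never enters the model.

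**Working it through.** **Inputs from the documents.** Arms of 60 and 40 (3.1); change from baseline as response; covariates age, sex and education (9.1). There is no plan figure to reproduce: the table of contents lists a sample-size section, but the body gives no calculation.

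**Assumptions.** Two-sided alpha 0.05; baseline-to-follow-up correlation r from 0.5 to 0.9; effects of 0.4 and 0.5 SD; one post-baseline visit (for example Week 12); the same variances and correlation in both arms. Outcome SD is set to 1.

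**1. Variance.** With equal variances at baseline and follow-up:

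- change score: 2(1-r)
- adjusted for baseline: 1-r²
- ratio, adjusted to change score: (1-r²)/[2(1-r)] = (1+r)/2

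The unadjusted sample size that matches 100 with adjustment is 100 divided by this ratio. If a comparison has 80% power on change scores, its expected z is 1.96 + 0.8416 = 2.8016. With adjustment the power is the normal probability below 2.8016/√ratio - 1.96. At r = 0.5 that argument is 3.235 - 1.96 = 1.275, which gives 90%.

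| r | Variance ratio | Unadjusted N matching 100 adjusted | 80% power becomes |
|---|---|---|---|
| 0.5 | 0.75 | 133 | 90% |
| 0.6 | 0.80 | 125 | 88% |
| 0.7 | 0.85 | 118 | 86% |
| 0.8 | 0.90 | 111 | 84% |
| 0.9 | 0.95 | 105 | 82% |

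**2. Power at 60:40 for assumed effects.**

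| r | 0.4 SD: unadjusted / adjusted | 0.5 SD: unadjusted / adjusted |
|---|---|---|
| 0.5 | 50.0% / 61.9% | 68.8% / 80.7% |
| 0.7 | 71.6% / 78.3% | 88.5% / 92.9% |
| 0.8 | 87.3% / 90.4% | 97.2% / 98.3% |

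**3. Chance imbalance.** The SD of the difference in baseline means is √(1/40 + 1/60) = 0.204. Given a baseline difference D, the unadjusted estimate shifts by -(1-r)D. For D = 0.204 the shift has size 0.102, 0.061 and 0.041 SD at r = 0.5, 0.7 and 0.8. The standard error of the change-score contrast is 0.204 × √[2(1-r)] = 0.204, 0.158 and 0.129. The shift is therefore 0.50, 0.39 and 0.32 of a standard error.

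**4. Do age, sex and education stand in for baseline?** If they explain a share R² of both scores, r is replaced by the partial correlation (r-R²)/(1-R²). With R² = 0.2 this is 0.375, 0.625 and 0.75 for r = 0.5, 0.7 and 0.8, and the ratios become 0.69, 0.81 and 0.88. These are lower than 0.75, 0.85 and 0.90, so under this model the relative gain from adding baseline grows.

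**5. Simulation (5,000 trials per setting, 60:40, three covariates, no treatment effect), r = 0.5, 0.7 and 0.8.** Variance ratios were 0.77, 0.86 and 0.92 with R² = 0, and 0.69, 0.82 and 0.88 with R² = 0.2. The slope of the unadjusted estimate on the baseline difference was -0.63, -0.38 and -0.26 with R² = 0.2, and about 0 after adjustment. Both estimators averaged about 0.

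**The case against.** **A change-score MMRM is a valid analysis.** This stands. Under randomization it is unbiased on average, and no inflation of type I error is shown. The imbalance point is conditional on the allocation actually drawn, so this is a matter of efficiency and robustness.

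**The size is not in the documents.** This also stands. At r = 0.9 the variance saving is 5%. At r = 0.8 with a 0.5 SD effect, power moves only from 97.2% to 98.3%.

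**The figures may not carry over to NAD+.** Sections 2.1.4 and 2.1.5 report rises of 35 to 168% and of 60%, so post-treatment variance may exceed baseline variance. With k = baseline SD / follow-up SD, the ratio is (1-r²)/(1+k²-2rk). At r = 0.5 it is 0.75 for k = 1, 0.95 for k = 0.7 and 1.00 for k = 0.5 (k values assumed). The gain can therefore vanish. It does not turn into a loss in large samples if the arms share the same covariance, because (1+k²-2rk) - (1-r²) = (k-r)², which is never negative. If NR raises the variance in one arm only, that bound is not guaranteed.

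**Baseline may be missing for some randomized participants.** The schedule in 6.1 marks randomization at Week 0, whereas 3.1 places it after the lead-in, so someone lost in between could lack a Week 2 value. FSS is not named at any visit, and its Week 2 collection is inferred from 6.2.2 and 10.2.1. Neither point affects the fix: a participant without a baseline value has no change score, so adding the covariate excludes nobody further.

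**The sponsor may have meant raw scores with Week 2 as a repeated response.** With free group and group-by-time terms, the arm means at baseline are unconstrained. With complete data, the contrast is again the unadjusted difference in change.

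**Conclusion.** The point holds. Section 9.1 omits the baseline value of the outcome, and nothing elsewhere in the document supplies it. For outcomes with similar variance at baseline and follow-up, adjustment would cut the variance of the treatment contrast by 25% at r = 0.5, 15% at r = 0.7, 10% at r = 0.8 and 5% at r = 0.9. It would also remove a conditional shift of about 0.3 to 0.5 standard errors for a typical (one-SD) chance imbalance at r = 0.8 to 0.5. These figures rest on assumed r, a single-visit contrast and equal variances; the gain for NAD+ may be smaller. The reading of the text is certain, but the size of the loss is not. The change is recommended because it costs almost nothing. The planned analysis is not invalid without it.

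**What to change.** Add to section 9.1: *The baseline (Week 2) value of the outcome and its interaction with visit are included as covariates.* The treatment difference is then the same whether the response is the change or the follow-up score, so the reported quantity does not alter. Make the change before unblinding, so that it is prespecified.

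The cost is one sentence and one baseline slope per post-baseline visit: two for RBANS and TMT-B (Weeks 12 and 22), four for ECog and NAD+ (Weeks 7, 12, 17 and 22). No visit, measurement or participant is added. For questionnaires also given at Week 0, that value could be a second covariate; this is optional and its benefit has not been quantified here.
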